2.2 Secondary objectives

1. To obtain preliminary data on the quality of glycemic control among the PC and EN groups, with separate analyses in the IP and TH sub-groups, and in the UC and iLet arms within those groups, which will be used to power a larger study with a glycemic control metric as the primary outcome. Our hypotheses are that glycemic control, with key outcomes being group mean CGM glucose, the group mean time with CGM glucose less than 54 mg/dl, and the group mean time with CGM glucose in the 70–180 mg/dl range, will be similar in the PC-IP group and the EN-IP group, and in the PC-TH group and the EN-TH group in the iLet arm. Additionally, we hypothesize that glycemic control will be similar in the PC-TH group and the PC-IP group, and in the EN-TH group and the EN-IP group in the iLet arm. Further, we hypothesize that there will be a larger difference in glycemic control metrics between the UC arms versus the iLet arm in the PC group than there will be in the EN group.
2. To assess the impact of the insulin-only configuration of the iLet bionic pancreas system on psychosocial outcomes (including quality of life, fear of hypoglycemia, and diabetes distress) among study participants. Secondary analyses will be conducted between the telehealth and in-

person arm, the EN and PC groups, and the iLet and UC arms.

3 Participant Selection

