6.7 Statistical Analyses

An intention-to-treat analysis will be performed. Descriptive statistics will be used to summarize patient characteristics and assessments. We will estimate the percentage of participants who have a mean sensor glucose <183 mg/dl in the iLet arms of all four groups (PC-IP, PC-TH, EN-IP, EN-TH), along with confidence intervals using the Clopper-Pearson method. The hypothesis is that there is no difference in the percentage of each group that meet this metric.

The primary analysis of the designated endpoints will be calculated on an intention-to-treat basis. In cases where an arm was not completed, we will use the available data from that arm in the data analysis. We will calculate percentages, means, standard deviations (and medians and interquartile ranges as appropriate), and ranges in descriptive analyses. Unless otherwise specified, continuous data will be summarized by presenting the number of non-missing observations, mean and standard deviation (SD) or median, minimum, and maximum. Categorical data will be summarized by presenting the number of patients and percentage for each category. We will use the t-test for comparisons of means for normally distributed outcomes and the Mann-Whitney U test for comparisons of medians on non-normally distributed outcomes between groups (PC-IP, PC-TH, EN-IP, EN-TH). We will use the paired t-test for comparison of means for normally distributed outcomes and the Wilcoxon Signed Rank test for comparisons of medians on non-normally distributed outcomes when comparing between iLet and usual care within groups. There will be no adjustments for multiple comparisons.

We may, in exploratory analyses, also stratify subjects for secondary analyses of the pre-specified endpoints by the following characteristics: sex, age, usual care insulin total daily dose, body mass index, baseline A1c, and use of CGM in usual care.

P-values can be displayed to aid interpretation, not for inference. Tables, figures and listings of all primary, secondary and safety endpoints will be created.

Data from periods when the bionic pancreas was not in use will be included, if available (Dexcom CGM data may not be available in some failure modes).

All questionnaire data (including quality of life data) for patients who have completed a minimum of 4 days with a device will be included. Results will be compared by Wilcoxon signed-rank test.

6.7.1 *Safety Analyses*

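### The hypothesis that the iLet benefit is larger in primary care than in endocrinology has no planned direct contrast or confidence interval

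*Combined protocol and SAP*

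**What the plan says.** Section 2.2, repeated in the Protocol Summary, expects that "there will be a larger difference in glycemic control metrics between the UC arms versus the iLet arm in the PC group" than in the EN group. The key metrics there are mean CGM glucose, time below 54 mg/dl and time in 70–180 mg/dl. The objective asks for preliminary data "among the PC and EN groups, with separate analyses in the IP and TH sub-groups", and says the data "will be used to power a larger study with a glycemic control metric as the primary outcome".

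Section 6.7 gives the methods for continuous outcomes:
- **Between groups:** a t-test for normally distributed outcomes, or a Mann-Whitney test "on non-normally distributed outcomes between groups (PC-IP, PC-TH, EN-IP, EN-TH").
- **Within groups:** a paired t-test or Wilcoxon signed-rank test "when comparing between iLet and usual care within groups".

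The only confidence intervals named are Clopper-Pearson intervals for the percentage of participants below 183 mg/dl in the iLet arm. Section 6.7 also says: "P-values can be displayed to aid interpretation, not for inference". Section 6.6 states that no power or sample size calculation was done.

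**The concern.** The hypothesis concerns a difference between two differences: the mean within-person effect in PC set against the mean within-person effect in EN. Neither planned tool is stated to estimate it. The unpaired test is described for outcomes across four cohorts, not for within-person changes in pooled PC against pooled EN. The paired test gives one result per group.

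What remains is to set two paired results side by side. A finding that PC is significant and EN is not would look like confirmation, and a finding that both are significant would look like no difference. Neither inference is sound, because each p-value depends on that group's own effect and noise and neither measures the gap between the effects.

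The stakes are modest. The hypothesis would be reported without an estimate of its own quantity or a statement of its uncertainty. A later trial that concerned differential benefit would lack a reported planning figure.

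**Working it through.** The plan gives no figure to reproduce for this contrast, so the check is an illustration for mean CGM glucose.

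**Inputs from the documents**
- SD of mean CGM glucose: 26 mg/dl under usual care and 13 mg/dl on the insulin-only iLet with lispro or aspart (bridging study; Table 2 and section 12.1.8).
- Means in that study: 163 and 155 mg/dl, a benefit of 163 − 155 = 8 mg/dl.
- 20 participants per practice (section 2.1).

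**Assumptions, not in the documents**
- Within-person correlation r = 0, 0.5 or 0.8.
- The same SDs in both practices.
- Two-sided 5% tests, normally distributed differences.
- Alternative true benefits of 15 and 30 mg/dl.

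**Step 1. SD of the within-person difference.** SD(D) = √(26² + 13² − 2r·26·13) = √(845 − 676r).
- r = 0: √845 = 29.1
- r = 0.5: √507 = 22.5
- r = 0.8: √304.2 = 17.4

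**Step 2. Equal true benefit in both practices.** Let p be the power of one paired t-test with n = 20 (noncentral t, 19 df, noncentrality = benefit ÷ (SD(D)/√20)). The practices are independent, so P(PC significant, EN not) = p(1 − p).

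| True benefit in both | r | p | PC only: p(1 − p) |
|---|---|---|---|
| 8 mg/dl | 0 | 0.215 | 0.17 |
| 8 mg/dl | 0.5 | 0.326 | 0.22 |
| 8 mg/dl | 0.8 | 0.495 | 0.25 |
| 15 mg/dl | 0 | 0.591 | 0.24 |
| 15 mg/dl | 0.5 | 0.807 | 0.16 |
| 15 mg/dl | 0.8 | 0.954 | 0.04 |

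A direct two-sample comparison of the differences would falsely favour PC about 2.5% of the time, which is half of its 5% two-sided error.

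**Step 3. Benefits that truly differ: 30 mg/dl in PC and 15 in EN.** P(both paired tests significant) is the product of the two powers. The PC test is significant with probability at least 0.99, so the EN test governs the product. The direct comparison has noncentrality 15 ÷ (SD(D)·√(2/20)) on 38 df.

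| r | Both paired tests significant | Power of the direct comparison |
|---|---|---|
| 0 | 0.59 | 0.36 |
| 0.5 | 0.81 | 0.54 |
| 0.8 | 0.95 | 0.76 |

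The paired pattern usually shows two significant results and says nothing about the 15 mg/dl gap. The direct test addresses the gap, but would miss it 64%, 46% or 24% of the time.

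**Step 4. Width of the direct interval.** Half-width = t(0.975, 38)·SD(D)·√(2/20) = 2.024 × SD(D) × 0.316.
- r = 0: 18.6 mg/dl
- r = 0.5: 14.4 mg/dl
- r = 0.8: 11.2 mg/dl

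**The case against.** The strongest reply is that little is lost. P-values are declared non-inferential. Section 6.7 plans tables and listings of the primary, secondary and safety endpoints, and section 6.7.3 plans de-identified individual listings. If the within-group tests cover pooled PC and EN, as section 2.2 implies, a reader can subtract the two effects, and with the individual listings could also derive the SD of the differences and an interval. The unpaired test could itself be applied to within-person differences.

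Much of this stands. The gap is one of specification: the information is not lost, and planning a later study is not blocked. But the text does not say that the unpaired test applies to differences, it names four cohorts where the hypothesis is about two practices, and it plans no interval. Two analysts could follow section 6.7 faithfully and only one would produce the contrast. Non-inferential p-values make an estimate with an interval more useful.

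The inputs are also open to challenge. The SDs come from days 3–7 of one study with 12 injection users and 22 pump users, whereas this trial averages days 3–14, PC is all injection users and EN is all pump users. Equal SDs across practices are therefore doubtful, and the probabilities are illustrative.

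A reader might infer that the false-support rate is the chance that exactly one practice is significant, 2p(1 − p), or 0.34, 0.44 and 0.50 at 8 mg/dl. The hypothesis is directional, and half of those cases are EN significant and PC not, which argues against it. The relevant rate is the one in Step 2.

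**Conclusion.** The point holds as a specification gap of low severity. The plan states a directional PC-versus-EN hypothesis about within-person benefit and names no analysis that estimates it. Under the stated assumptions, relying on two paired tests would give false support in 4% to 25% of trials with equal benefit, against about 2.5% for a direct comparison. A direct comparison corrects the logic but does not make the trial decisive: its power for a 15 mg/dl gap is 0.36 to 0.76.

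Two stronger readings are not supported. A reader might infer that the trial's main conclusion is at risk. It is not: the primary endpoint is a percentage per group with its own interval, and the trial claims no power. A reader might also infer that the non-randomized iLet-arm comparisons must be adjusted for baseline HbA1c. The similarity hypotheses in section 2.2 concern the groups as recruited, so an adjusted estimate would ask a different question and would still leave PC and EN confounded with site and prior therapy. The documents give no figures from which to size any shift, so adjustment is a matter of preference.

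**What to change.** Add to section 6.7, for mean CGM glucose, time in 70–180 mg/dl and time below 54 mg/dl:
- Compute each participant's iLet-minus-usual-care difference over days 3–14.
- Report the PC-minus-EN difference (20 v 20) with a 95% confidence interval, using the Welch t method for mean glucose and time in range.
- For time below 54 mg/dl, which is likely to be skewed, use a Hodges-Lehmann or bootstrap interval. A Mann-Whitney p-value alone would give neither an estimate nor an interval.
- Label the result descriptive, and state that PC versus EN cannot be separated from site and prior therapy.
- State the expected half-width for mean glucose, about 11 to 19 mg/dl, with its assumptions.

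The cost is a few sentences and slightly more analysis. No new data, visits or participants are needed. The drawback is a wide interval that may well include zero even if a real gap exists.

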5.6.1.2.2 UC arm

- No modifications will be made to dosing regimens for participants in the usual care arm.
- Study staff will confirm the participant is wearing the study CGM, and answer any questions the participant may have about the CGM. They will remind the participant to replace the study CGM after 10 days.

5.6.1.3 Crossover Visit (Visit 5):

- At the end of the first study period (Day 14 [+2]), participants will return to the clinic and answer the post questionnaires for the study arm.
- A urine pregnancy test will be performed in participants of child-bearing potential. If the test is positive, the participant will be informed of the result and the next planned study arm will not proceed. The date of the last menstrual period will also be documented.
- Any changes to medications or medical history and any adverse events that may have occurred since the last study visit will be documented.

- All study devices applicable to the arm just completed will be downloaded
 - BP arm: iLet and study glucometer and ketone meter
 - UC arm: Dexcom G6 and study glucometer
- Participants will repeat psychosocial questionnaires (including quality of life, fear of hypoglycemia, diabetes distress).
 - Participants coming off of the BP arm will be asked to complete the Bionic Pancreas User Opinion Survey
- Participants will then start over with Day 1 procedures for the arm they are randomized to next. This may occur immediately, or within 14 days after the completion of the first arm.
 - If the participant is switching from usual care to bionic pancreas:
 - If using an insulin pump (EN group), their own insulin infusion pump will be stopped and disconnected if applicable, and its infusion set will be removed
 - If using MDI therapy (PC group), they will be instructed not to take any additional insulin injections once the bionic pancreas is started, unless instructed to do so by study staff
 - If the participant is switching from bionic pancreas to usual care, a provider (MD or NP) will review the last several hours of insulin dosing and assist the participant in resuming their usual care.
 - For participants whose usual care is MDI therapy:
 - If normal long-acting dose time is MORNING:
 - Morning study visit – take full dose at visit, take next day dose at usual time
 - Afternoon study visit – three quarters of normal dose at visit, take next day dose at usual time
 - If normal long-acting dose time is EVENING:

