6.1 Data Collected

6.1.1 *Prior to the start of the experiment:*

- Age
- Sex
- Race and ethnicity

- Basic demographic information
- Date of last menstrual period in pre-menopausal participants
- Approximate date of diabetes diagnosis
- Medical, surgical, and social history, allergies and review of systems relevant to inclusion and exclusion criteria
- Medications (prescription and non-prescription) and date of last change in medication regimen
- Duration of insulin pump and CGM use, if applicable
- Type of insulin(s) currently used
- Insulin regimen (basal rate, sensitivity factor, and carbohydrate ratio for pump and if known for MDI; otherwise doses and schedule for MDI, sliding scale/correction if applicable)
- Average total daily dose of insulin in the last 30 days from pump data and/or self-reported estimate from MDI patient report
- Usage of CGM (type of CGM, days per month worn, usage of data, whether insulin dosing is based on CGM alone, alarm settings), if applicable
- Height and weight (height will be self-reported for TH participants)
- Urine HCG (pre-menopausal participants)
- Hemoglobin A1c

6.1.2 *During study arms*

- CGMG (CGM glucose) every five minutes from the Dexcom CGM
- All fingerstick BG measurements taken by the participant (meter download)
- Average glucose target used
- Insulin total daily dose from bionic pancreas download
- Timing of meal announcements and size of meals announced from bionic pancreas download
- Time participants were not under bionic pancreas control
- Information collected from the daily survey:
 - Number of reported hypoglycemic events requiring carbohydrate intervention
 - Total grams of carbohydrates taken to prevent or treat hypoglycemia
 - Number of severe hypoglycemic events (defined as participant required assistance to treat)
 - Number of unscheduled insulin cartridge/infusion set changes
 - Time disconnected from the iLet (for participants on the BP arm)
- Data from questionnaires about quality of life, attitudes and expectations regarding the bionic pancreas at baseline and on day 14 of each arm.
- Number of and reasons for unscheduled visits and phone calls
- Device malfunctions requiring study team contact and other reported device issues
- Type of automation used, if any, by participants in the EN group

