6.5 Other endpoints

- The percentage of time that valid CGM glucose readings are captured by the iLet
- The percentage of the time that the insulin pump channel of the iLet is available
- Percentage of time across days 3-14 within each of the following CGM glucose ranges:
 - < 70 mg/dl
 - > 180 mg/dl
 - > 250 mg/dl
- Percentage of time participants were disconnected from the iLet
- Number of episodes of symptomatic hypoglycemia (reported daily by participants)
- Percentage of participants with mean Dexcom CGMG <154 mg/dl (estimated average glucose corresponding to an A1c of <7.0%) on days 3-14
- Mean total daily dose of insulin in the iLet arms and in the usual care arms of the EN groups (from pump download) on days 3-14
- Mean daily basal insulin dose in the iLet arms and in the EN groups' usual care arms (from pump download) on days 3-14
- Mean daily bolus insulin dose in the iLet arms and in the EN groups' usual care arms (from pump download) on days 3-14
- Mean number of daily meal announcements in the iLet arms and meal boluses in the EN groups' usual care arms (from pump download) on days 3-14
- Glucose variability measured with coefficient of variation (CV) and with mean of daily difference (MODD) on days 3-14
- Number of unscheduled insulin cartridge/infusion set changes in the iLet arms
- Mean glucose target in the iLet arms
- Scores from psychosocial questionnaires (including quality of life, fear of hypoglycemia, and diabetes distress). These surveys will be collected at baseline and after each arm. Post-BP measurements, including the bionic pancreas user opinion survey, will be given only after the BP arm.

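### The four-day device minimum for questionnaires departs from the plan's own intention-to-treat rule and can drop the earliest iLet stoppers from the psychosocial analysis

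*Combined protocol and SAP*

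**What the plan says.** Section 6.7 gives a general rule: "The primary analysis of the designated endpoints will be calculated on an intention-to-treat basis". It adds that an arm cut short still contributes the data it produced. Further down, questionnaires get their own rule: "All questionnaire data (including quality of life data) for patients who have completed a minimum of 4 days with a device will be included". They are then compared by Wilcoxon signed-rank test. The section gives no reason for four days, no definition of device, and no missing-data rule or sensitivity analysis for questionnaires.

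The second secondary objective in section 2.2 begins: "To assess the impact of the insulin-only configuration of the iLet bionic pancreas system on psychosocial outcomes". It names comparisons of telehealth with in-person care, EN with PC, and iLet with usual care. Section 6.5 lists the scores among the other endpoints.

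On timing, section 6.5 says "These surveys will be collected at baseline and after each arm", and section 6.1.2 lists "Data from questionnaires about quality of life, attitudes and expectations regarding the bionic pancreas at baseline and on day 14 of each arm". Sections 5.6.1.3, 5.6.1.4, 5.6.2.3 and 5.6.2.4 place the post-baseline forms at the crossover and final visits. The user opinion survey follows the iLet arm only: "Post-BP measurements, including the bionic pancreas user opinion survey, will be given only after the BP arm". No form is scheduled for the moment a participant stops the iLet. Section 5.7.2 returns such a participant to pre-study therapy, and section 9.2 uses the data of those who withdraw up to the time of withdrawal.

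**The concern.** Whether a person reaches four days on the iLet is known only after randomisation and may depend on how they get on with it. Section 5.7.2 foresees stopping by the participant's own choice. Section 9.2 ends iLet use after severe hypoglycemia, or after DKA that requires hospitalization. On the natural reading of the rule, someone who stops for any of these reasons in the first three days adds nothing to the fear-of-hypoglycemia, distress or quality-of-life results.

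The filter has little to act on in usual care, where nobody has to persist with an unfamiliar therapy. The signed-rank test is paired, so losing the iLet score loses the person. The trial has four groups of 10 and asks whether pump-naïve users can be started on the device, so the reactions of those who could not continue are part of the answer.

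**Working it through.** **1. Is there a planned figure to reproduce?** No. Section 6.6 states that no power or sample-size calculation was done, and the documents give no dropout rate and no questionnaire SD.

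**2. Whom does the rule affect?** Setting sections 6.7, 5.6, 5.7.2 and 9.2 side by side:

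| Participant in the iLet arm | End-of-arm form | Device = iLet | Device = any, including study CGM |
|---|---|---|---|
| Stops on day 2 or 3, stays in study | Due at crossover or final visit | Left out, even if completed | Kept |
| Stops on day 5, stays in study | Due about 14 − 5 = 9 days later | Kept | Kept |
| Withdraws from the study during the arm | None | Nothing to include | Nothing to include |

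Only in the first row does the four-day rule itself change the analysis. There it contradicts the general rule on incomplete arms. By comparison, the exploratory analyses in section 6.7.4 ask for only 24 hours of CGM data.

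**3. Size of the shift.** Let k of N be excluded, with mean change E, and let the rest have mean change R. The mean of all is [(N − k)R + kE]/N. The filtered analysis reports R, so the shift is R − mean of all = (k/N)(R − E) = (k/N) × D. With D assumed at 0.5, 1 and 2 SD:

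| k of N | D = 0.5 | D = 1 | D = 2 |
|---|---|---|---|
| 1 of 10 | 0.05 | 0.10 | 0.20 |
| 2 of 10 | 0.10 | 0.20 | 0.40 |
| 1 of 20 | 0.025 | 0.05 | 0.10 |
| 2 of 20 | 0.05 | 0.10 | 0.20 |
| 2 of 40 | 0.025 | 0.05 | 0.10 |

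**4. Chance that it arises.** With an assumed early-stop rate d, the chance of at least one exclusion is 1 − (1 − d)^N. For d = 2.5%, 5% and 10% this gives 22%, 40% and 65% in a group of 10, and 64%, 87% and 98.5% among all 40. The one iLet completion figure found in the documents is from the adult bridging study (Table 2): 34 of 36 completed, so 2/36 = 5.6% were lost over three 7-day arms. Scaled to this trial, that is 40 × 2/36 = 2.2 people at any time. When those two left, and from which arm, is not given.

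**5. Dependence on the reason for stopping.** A simulation with no true difference dropped the least tolerant participants, with correlation rho between tolerance and score. At rho = 0, 0.5 and 1 the apparent iLet advantage was 0.00, 0.09 and 0.17 SD for one dropped of 10, and 0.00, 0.05 and 0.10 SD for two dropped of 40.

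**The case against.** **The exclusion is implied.** The rule says who is included, speaks of patients rather than arms, and does not name the iLet. Everyone wears a study Dexcom G6 in both arms, and EN participants use their own pumps in usual care. If these count, a day-3 iLet stopper passes. This stands as a caveat. But on that reading the rule would exclude hardly anyone, so the text needs settling either way.

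**The direction is assumed.** Stopping can also follow intercurrent illness (section 4.1), investigator judgement (sections 5.7.2 and 9.2) or pregnancy (section 9.2). This stands: a reader might infer that the rule necessarily flatters the iLet, and the documents do not show that.

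**A large multiple is tempting.** Suppose those who continue gain 0.5 SD and early stoppers lose 1.0 SD. One or two stoppers in 10 then give true means of 0.35 and 0.20 SD against a reported 0.50, which are ratios of 1.43 and 2.5. The documents do not support this:
- It needs 10 to 20% of one group of 10 to stop before day 4, whereas the bridging study lost 5.6% in total.
- The comparisons named in section 2.2 rest on 20 or 40 people. The same effects give 0.50/0.425 = 1.18 and 0.50/0.35 = 1.43 in 20, and 0.50/0.4625 = 1.08 and 0.50/0.425 = 1.18 in 40.
- The effects themselves are invented.

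**Later stoppers.** A reader might fault the day-14 score of a day-5 stopper for reflecting usual care. Scoring at the scheduled time regardless of adherence is what intention-to-treat means, so this is no defect. Nor do the documents say that such people go unsurveyed: section 5.7.2 does not cancel their later visits, and the visit schedule allows arm length to vary and a separate shutdown visit.

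**Differences between groups.** One might expect more early stopping in PC or telehealth. No stop rate by group is given, so a larger bias there is conjecture.

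**Mitigations.** P-values are an aid to interpretation only, discontinuations are tabulated with reasons, and individual listings are planned. These lower the weight of the point, but a mean over a filtered set is shifted whether or not a p-value is attached.

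**Conclusion.** The point holds as an internal inconsistency with a possible bias of unknown size. Section 6.7 applies an exposure filter that its own rule on incomplete arms would not allow. If device means the iLet, the filter removes the earliest stoppers from the outcomes of a secondary objective. The results lean towards the iLet only if those people score worse than the others. On the assumptions shown, one or two exclusions move a mean by a few hundredths of an SD in all 40, and by 0.05 to 0.40 SD in a group of 10. With no exclusions, or with stopping unrelated to the score, the shift is zero. The consequence is moderate: the outcomes are not primary and the inference is descriptive, but the correction is nearly free.

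**What to change.** In section 6.7:
- Make the main questionnaire analysis all available questionnaires from participants who started the arm, in line with the stated intention-to-treat rule.
- Keep the set with at least four days as a sensitivity analysis, with device defined as the iLet in the iLet arm.
- Report excluded or missing scores by arm and group, with reasons.

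In sections 5.6 and 5.7.2:
- State that participants who stop the iLet but remain in the study still complete the scheduled end-of-arm questionnaires.
- Offer them the existing forms, including the user opinion survey, at the time of stopping. Treat these as supplementary data, analysed separately from the scheduled score; they should not replace it.

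The cost is a few sentences of wording and existing forms given once more to the few who stop. The drawback is that some scores will reflect short exposure, which the sensitivity set addresses. The collection part has to be settled before conduct, because forms never given cannot be recovered at analysis.

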6.4 Safety endpoints

- Frequency of adverse events
- Frequency of severe hypoglycemia
- Frequency of diabetic ketoacidosis, as defined within this protocol in Section 9.2.

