No inferential tests of safety data will be performed. Descriptive summaries of safety data will be presented. Treatment-emergent AEs are defined as AEs with onset date on or after the first day of exposure to randomized treatment.

6.7.2 *Baseline Descriptive Statistics*

The number and percentage of patients who were screened, randomized, discontinued (with reason for discontinuation), and completed the trial will be summarized descriptively for all screened patients. Baseline and demographic data will be summarized using descriptive statistics. All comparisons will be between treatments within patients. Listings of de-identified individual patient data will be presented.

6.7.3 *Tabulation of Individual participant Data*

Listings of de-identified individual patient data will be presented.

6.7.4 *Exploratory Analyses*

The performance of the iLet in each period can be compared with historical data from previous bionic pancreas trials. If the performance of the iLet in this study is comparable to our previous data, that will support the hypothesis that the iLet can be safely used in primary care settings and via telehealth. All participants with at least 24 hours of CGM data during days 3-14 of any treatment periods will be included in these analyses.

7 Risks and Discomforts

Participants may experience mild discomfort associated with the insertion of infusion sets and the Dexcom CGM sensor into the SC tissues. The risk of discomfort due to insertion of infusion sets and sensors may be greater than in their lives outside the trial because more infusion sets and sensors are required than are used in usual care, and some participants will have only used MDI.

There is a risk of hypoglycemia. This risk is expected to be similar to or less than the risk during the participants' lives outside of the trial based on data from earlier trials. All of our previous studies have shown that hypoglycemia is reduced in all configurations of the bionic pancreas when compared with usual care.

There is a risk of hyperglycemia. This risk is expected to be less than the risk during the participants' lives outside of the trial based on data from earlier trials. All of our previous studies have shown that hyperglycemia is significantly reduced in all configurations of the bionic pancreas when compared with usual care.

8 Potential Benefits

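### Section 6.7.4 lets an undefined comparable result support a hypothesis of safe use, and Section 6.7.1 plans no confidence limits for severe hypoglycemia or DKA

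*Combined protocol and SAP*

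**What the plan says.** Section 6.7.4, under Exploratory Analyses, opens with an optional comparison: "The performance of the iLet in each period can be compared with historical data from previous bionic pancreas trials". It then says that if performance "is comparable to our previous data, that will support the hypothesis that the iLet can be safely used" in the two new settings. The only other rule there is an analysis set: "All participants with at least 24 hours of CGM data during days 3-14 of any treatment periods will be included in these analyses".

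The safety endpoints in Section 6.4 are the frequencies of adverse events, severe hypoglycemia and DKA. Section 6.7.1 says of them: "No inferential tests of safety data will be performed. Descriptive summaries of safety data will be presented". By contrast, Section 6.7 reports the primary percentage (mean glucose below 183 mg/dl) by group "along with confidence intervals using the Clopper-Pearson method".

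Section 9.2 stops the iLet for a participant who has severe hypoglycemia, or DKA requiring hospitalization, in the iLet arm. If more than one participant is stopped for these reasons, other than through deliberate misuse, randomization halts until the DSMB votes to restart.

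**The concern.** I found no other analysis sentence that leads from data to a statement about safe use, and its criterion is the word *comparable*. Nobody can say in advance which result would fail it. The sentence also concerns overall performance, while the events that bear most directly on safety are tabulated without any indication of what a low or zero count rules out.

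Safety is in the study title, and Section 8 expects the trial to add knowledge about safety in care models not tested before. A report of no severe events and results similar to earlier trials would be read as reassurance. With 20 people per setting followed for 14 days, that reassurance is weak, and the plan does not require the report to show how weak.

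**Working it through.** Section 6.6 states that no power or sample size calculation was done, and no margin is given, so there is no figure of the plan's own to reproduce.

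**Inputs.**
- 40 participants in four groups of 10 (Section 2.1). This gives 20 in primary care, 20 in telehealth, and 30 in a care model that Section 8 calls untested (PC-IP, PC-TH and EN-TH).
- 14 days on the iLet each (Section 2.1).
- Closest earlier arm: adult bridging study, insulin-only iLet with lispro or aspart, 155±13 mg/dl, n=34 (Table 2).
- The plan states no confidence level; I assume 95%.

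**Zero events.** The exact two-sided upper limit is 1 − 0.025^(1/n); the one-sided limit is 1 − 0.05^(1/n). The last column is the chance of seeing no event if the true 14-day risk were 5%, which is 0.95^n.

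| People | Two-sided upper limit | One-sided upper limit | P(0 events) at 5% risk |
|---|---|---|---|
| 10 (one group) | 30.8% | 25.9% | 59.9% |
| 20 (one setting or visit mode) | 16.8% | 13.9% | 35.8% |
| 30 (new care models) | 11.6% | 9.5% | 21.5% |
| 40 (all) | 8.8% | 7.2% | 12.9% |

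As a rate, 40 × 14 / 365.25 = 1.53 person-years. Zero events leaves a two-sided upper limit of −ln(0.025) / 1.53 = 2.41 events per person-year.

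**The pause rule in Section 9.2.** It acts at two or more of 40. P(≥2) = 1 − (1−p)^40 − 40p(1−p)^39, which gives:
- p = 1%: 6.1%
- p = 2.5%: 26.4%
- p = 5%: 60.1%
- p = 10%: 92.0%

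One participant stopped out of 40 would not trigger the rule, yet has an exact two-sided upper limit of 13.2%.

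**Mean glucose against the bridging arm.** The 95% half-width is 1.96 × √(13²/34 + SD²/n). With SD 13 it is 9.2 mg/dl for 10 people, 7.2 for 20 and 5.9 for 40. Earlier adult insulin-only arms with lispro or aspart at targets of 110 to 130 mg/dl have SDs of 9 to 17 (Tables 1 and 2). Over that range the half-width for 20 people runs from 5.9 to 8.6 mg/dl. So even with identical observed means, a setting of 20 people could not exclude a difference of about 7 mg/dl.

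**Choice of reference.** The same earlier arms have means from 148 to 161 mg/dl, so *comparable* depends on which one is picked. Tables 1 and 2 report time below 60 mg/dl, whereas this trial's endpoints are below 54 and below 70 mg/dl. I found no severe-event rate for any earlier study in the documents, so there is nothing there to compare the severe events with.

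**The case against.** The case on the other side has real weight. The comparison is optional, exploratory, and said only to support a hypothesis, in a trial that Section 6.6 describes as mainly one of feasibility. Severe events are not unlimited: Section 9.2 has individual stopping, a pause at two participants and an external DSMB. Counts will be tabulated, so a reader could work out exact limits. And a confidence interval against an earlier arm does not remove non-random differences between studies.

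These points rule out several stronger readings that a reader might infer:
- **That the plan will declare the iLet safe, or that clearly worse results would pass.** The text only fails to prevent this; nothing says such results would be called comparable.
- **That severe events have no limit at all.** The pause rule is a limit, though one on conduct, set across the whole study and not per care model.
- **That a favourable conclusion would be reached most of the time despite real harm.** At a true 5% risk, zero events is seen 36% of the time in 20 people and 13% in 40. It exceeds half only in a single group of 10, and the sentence in 6.7.4 is about primary care and telehealth, which have 20 each.
- **That *comparable* means not significantly different.** The plan does not say so, and that reading sits badly with "P-values can be displayed to aid interpretation, not for inference". Under it, if true control equalled the bridging study's usual-care mean (163 mg/dl), the chance of no significant difference runs from about 43% to 86%, depending on group size (10 or 20), SD (13 or 26) and version of the t-test. No single figure should be quoted.

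What remains is that the sentence in 6.7.4 has no stated criterion, that the pause rule is not connected to it, and that leaving readers to derive the limits does not stop a safety statement being made without them. Section 6.7.1 is no obstacle: "No inferential tests of safety data will be performed" excludes tests, and an interval is not a test.

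**Conclusion.** The point holds as a weakness in how safety would be reported. A result with no defined criterion may be cited in support of safe use, and the severe-event proportions carry no confidence limits. With zero events the data would still be compatible with a 14-day risk of up to 16.8% in either new setting, 11.6% across the new care models and 8.8% overall. Absence of events, or a mean glucose close to an earlier trial's, is therefore not evidence of safety on its own.

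The figures assume a two-sided 95% level, participants counted once each, and all 40 completing 14 iLet days; fewer completers would widen every limit. The glucose half-widths also assume the bridging arm as reference and the SDs shown. The correction should be made, but it does not call into question the feasibility aim or the primary endpoint.

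**What to change.** **Section 6.7.1.** Add exact Clopper-Pearson 95% intervals for the proportion of participants with at least one severe hypoglycemia event, and with at least one DKA event, in the iLet arm. Report them for all participants and separately for PC, EN, TH and IP, and give the upper limit wherever safety is discussed.

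**Section 6.7.4.** Replace the sentence on comparable performance with wording such as:

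> The difference in each named CGM metric between the iLet arm and one named earlier arm will be reported descriptively with a 95% CI. Statements about safety will be limited to what the upper confidence limits for severe events exclude. Absence of a difference, or of events, will not be taken as evidence of safety.

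The bridging study's lispro/aspart arm (155±13 mg/dl, n=34) is one candidate for the reference. The text should note that it ran for 7 days with Eversense or Dexcom G5 sensors, whereas this trial runs for 14 days with the G6, so the interval reflects sampling error only.

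**Cost.** A few more intervals by a method the plan already names, and a more modest safety statement. No extra participants, visits or tests are needed.
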